16.1.2.2 Planned Avelumab PK Outputs

The following listings and summary statistics of avelumab PK concentration and parameter data will be provided, where data permit:

- Individual values and summary of avelumab serum concentrations ($\mu\text{g/mL}$) by dose level, cycle, day, and scheduled time point
- Individual values and summary of single dose PK parameters for avelumab by dose
- Individual values and summary of avelumab C_{EOI} and C_{trough} by dose level
- Summary of avelumab serum concentrations ($\mu\text{g/mL}$) by dose level, cycle, day, and scheduled time point, stratified by weight (<10 kg or ≥ 10 kg)
- Summary statistics of single dose PK parameters for avelumab, stratified by weight (<10 kg or ≥ 10 kg)
- Summary statistics of C_{EOI} and C_{trough} by dose level, stratified by weight (<10 kg or ≥ 10 kg)
- Individual serum concentration-time course (linear and semi-logarithmic scales) by phase, dose level/cohort, cycle, and day, using actual time points (where available)
- Arithmetic mean serum concentration-time course on both linear ($\pm\text{SD}$) and semi-logarithmic scales using scheduled time points – with all dose levels overlaid on the same plot for the single dose in Cycle 1, stratified by weight (<10 kg or ≥ 10 kg)
- Arithmetic mean trough concentration-time course will be plotted on linear ($\pm\text{SD}$) scale using scheduled time points – with all dose levels overlaid, stratified by weight (<10 kg or ≥ 10 kg)

Dose proportionality (if appropriate) will be presented graphically as follows:

- Boxplots for dose-normalized PK parameters (AUC/Dose , C_{max}/Dose and C_{EOI}/Dose) by dose level, stratified by weight (<10 kg or ≥ 10 kg).

- Scatter Plot of individual AUC, C_{max} , and C_{EOI} versus Dose on a log-log scale. A linear regression may also be overlaid.

16.1.3 Population PK Analysis

The population PK analysis plan will be specified in a separate document.

16.2 Immunogenicity (Secondary Endpoint)

Analysis Set: Immunogenicity analysis set

Blood samples for ADA analysis will be collected predose (within 2 hours prior to study treatment) during Cycles 1, 2, 3, 5, 7, 13, 19, 25, and every 6 cycles thereafter for as long as the subject is receiving study treatment; and at the 30-day Safety Follow-up Visit. If the sample is positive for ADA, it will be re-analyzed to determine the titer and tested for neutralizing capacity. The ADA results will be derived based on the algorithm in Table 6. Subjects will be characterized into different ADA categories based on criteria in Table 7.

Table 6 Algorithm for the Derivation of ADA Results

Sample Screen Result in SDTM	Confirmatory Result in SDTM	Titer Result in SDTM	ADA Result in ADaM
Negative	NA	NA	Negative
NR	NA	NA	NR
Positive	Negative	NA	Negative
Positive	NR	NA	NR
Positive	Positive	Number	Number
Positive	Positive	NR	Positive-TNR

NR = no result, NA = not applicable, TNR = titer no result.

Negative, number, or positive-TNR are valid results, while number and positive-TNR are considered as positive.

Table 7 Subjects Characterized based on ADA Results

Category	Definition	Subject at Risk (Denominator for Incidence)
Never positive	No positive results at any time point	Number of subjects with at least one valid result at any time point
Ever positive	At least one positive result at any time point	Number of subjects with at least one valid result at any time point
Pre-existing	A positive ADA result prior to treatment with avelumab	Number of subjects with valid baseline result
Treatment boosted	A positive ADA result prior to treatment with avelumab and the titer ≥ 8 *baseline titer while on avelumab treatment	Number of subjects with valid baseline and at least one valid post-baseline result
Treatment emergent	Not positive prior to treatment with avelumab and with at least one positive post-baseline result	Number of subjects with at least one valid post-baseline result and without positive baseline results (including missing, NR)
Transient positive	If treatment emergent subjects have (a single positive evaluation, or duration between first and last positive result <16 weeks) and last assessment not positive.	Number of subjects with at least one valid post-baseline result and without positive baseline results (including missing, NR)
Persistent positive	If treatment emergent subjects have duration between first and last positive result ≥ 16 weeks or a positive evaluation at the last assessment	Number of subjects with at least one valid post-baseline result and without positive baseline results (including missing, NR)

Samples with a reportable ADA titer will also be tested in the neutralizing antibody (nAb) assay. nAb results are Positive or Negative in a single assay and only derived when not performed because ADA negative (see Table 8). Subjects will be characterized into different nAb categories based on the criteria in Table 9. For nAb, treatment-boostered is not applicable since no titer result.

Table 8 Algorithm for the Derivation of nAb Results

ADA Confirmatory Result in SDTM	nAb Result in SDTM	Derived nAb Result in ADaM
Negative	NA	Negative
NR	NA	NR
NA	NA	Negative
Positive	NR	NR
Positive	Positive	Positive
Positive	Negative	Negative

ADA = antidrug antibody, NA = not applicable, nAb = neutralizing antibody, NR = no result. Positive or Negative are considered valid results.

Table 9 **Subjects Characterized based on nAb Results**

Category	Definition	Subject at Risk (Denominator for Incidence)
Never positive	No nAb positive results at any time point	Number of subjects with at least one valid ADA result at any time point
Ever positive	At least one nAb positive result at any time point	Number of subjects with at least one valid ADA result at any time point
Pre-existing	A positive nAb result prior to treatment with avelumab	Number of subjects with valid ADA baseline result
Treatment emergent	Not nAb positive prior to treatment with avelumab and with at least one nAb positive post-baseline result	Number of subjects with at least one ADA valid post-baseline result and without nAb positive baseline results (including missing, NR)
Transient positive	If treatment emergent subjects have (a single nAb positive evaluation, or duration between first and last nAb positive result <16 weeks) and last ADA assessment not nAb positive.	Number of subjects with at least one ADA valid post-baseline result and without nAb positive baseline results (including missing, NR)
Persistent positive	If treatment emergent subjects have duration between first and last nAb positive result ≥16 weeks or a nAb positive evaluation at the last ADA assessment	Number of subjects with at least one ADA valid post-baseline result and without nAb positive baseline results (including missing, NR)

ADA = antidrug antibody, nAb = neutralizing antibody, NR = no result.

[figure not shown]
The frequency and percentage of each ADA and nAb category will be presented in tables by dose level and overall.

A listing will be prepared for all ADA ever-positive subjects including the following details: subject ID, dose level, age, gender, ADA Status, Study Day of Start of ADA response, Duration of ADA immunogenicity response (weeks), nAb Status, Study Day of Start of nAb response, Duration of nAb immunogenicity response (weeks)

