### 7.6.3 Antidrug Antibody

An overview of human ADA immunogenicity assessments (including neutralizing antibodies [NAbs]) planned in the trial is provided in the Schedule of Assessments - PK and ADA Sampling (see [Table 2](#)).

A blood sample for baseline ADA analysis will be collected within 2 hours prior to trial treatment administration on Cycle 1 Day 1. Further blood samples for ADA analysis will be collected predose (within 2 hours prior to trial treatment) during Cycles 2, 3, 5, 7, 13, 19, 25, and every 6 cycles thereafter for as long as the subject is receiving trial treatment; at the End of Treatment

Visit; and at the 30-day Safety Follow-up Visit. Samples positive for ADA will be re-analyzed to determine the titer and tested for neutralizing capacity.

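### SAP 16.2, neutralizing antibodies: Table 9 counts ADA-positive subjects with no nAb result as never positive, Table 8 turns a screening no-result into nAb Negative, and the text is inconsistent on which samples are tested

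*SAP*

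**What the plan says.** SAP 16.2 derives the ADA result of each sample in Table 6 and the nAb result in Table 8, then classifies subjects on nAb in Table 9.

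- **When nAb is derived.** The text before Table 8 says that nAb results come from a single assay and are "only derived when not performed because ADA negative (see Table 8").
- **Table 8.** It uses the ADA confirmatory result and the nAb assay result; the screening result is not an input. One row reads "NA NA Negative" and another "Positive NR NR". Its note adds: "Positive or Negative are considered valid results".
- **Valid ADA results.** The note to Table 6 says: "Negative, number, or positive-TNR are valid results, while number and positive-TNR are considered as positive". TNR means that the titer gave no result.
- **Which samples are tested.** The text before Table 8 says: "Samples with a reportable ADA titer will also be tested in the neutralizing antibody (nAb) assay". Protocol 7.6.3 says: "Samples positive for ADA will be re-analyzed to determine the titer and tested for neutralizing capacity". The opening paragraph of SAP 16.2 agrees with the protocol.
- **Table 9.** Never positive is defined as "No nAb positive results at any time point". The denominator for never and ever positive is the subjects with a valid ADA result. The transient and persistent rows depend on whether the last ADA assessment was nAb positive.

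**The concern.** Immunogenicity including neutralizing antibodies is a named secondary endpoint, and SAP 16.2 tabulates the frequency and percentage of each nAb category by dose level and overall. Those tables should keep a measured negative apart from an absent result. Two rules do not. A sample whose screening assay failed leaves Table 8 with a valid nAb Negative. A subject who is ADA positive but has no nAb result on any ADA-positive sample leaves Table 9 as never positive. The second error can only push the ever-positive percentage down. With 12 to 36 subjects planned for Phase I, one subject is visible in the percentage. The disagreement over positive-TNR samples could add to the number of subjects without a nAb result.

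**Working it through.** The plan states no nAb rate or count, so there is no figure to reproduce. The check is to run Tables 6, 8 and 9 against each other.

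**Step 1: Table 6 against Table 8, for each sample type.**

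| Screen | Confirmatory | Titer | nAb assay | ADA result (Table 6) | nAb result (Table 8) |
|---|---|---|---|---|---|
| Negative | NA | NA | NA | Negative | Negative |
| NR | NA | NA | NA | **NR** | **Negative** |
| Positive | Negative | NA | NA | Negative | Negative |
| Positive | NR | NA | NA | NR | NR |
| Positive | Positive | number | Positive or Negative | number | as assayed |
| Positive | Positive | number | NR | number | NR |
| Positive | Positive | NR | NR | Positive-TNR | NR |
| Positive | Positive | NR | NA (not run) | Positive-TNR | no row |

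The second line is the error: the ADA result is not valid, yet the nAb result is a valid Negative. The sample is not ADA negative, so the text does not allow a derivation. The last line is a gap in Table 8.

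**Step 2: does the Table 8 error move incidence?** Table 9 numerators need a positive nAb result and its denominators need valid ADA results. Changing a screen-NR sample from nAb Negative to NR touches neither. To confirm this, I enumerated eight sample states (positive-TNR taken as Table 8's Positive/NR row) over baseline and three later visits, assumed at weeks 4, 12 and 24. Of 8^4 = 4,096 sequences, 2^4 = 16 have no valid ADA result, which leaves 4,080. Correcting Table 8 alone changes ever, never, pre-existing and treatment-emergent status, and every denominator, in 0 of 4,080.

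**Step 3: Table 9 never positive.** Sequences with an ADA-positive sample but no nAb result on any such sample number 6^4 − 4^4 = 1,296 − 256 = 1,040. All 1,040 are classed as never positive and stay in the denominator. For N subjects, x of them nAb positive and u ADA positive but untested:

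- as written: x/N
- untested excluded: x/(N − u)
- upper bound: (x + u)/N

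N is set at the two ends of the planned Phase I range (Protocol 5.1.1); x and u are assumed.

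| N | x | u | As written | Untested excluded | Upper bound |
|---|---|---|---|---|---|
| 12 | 1 | 1 | 1/12 = 8.3% | 1/11 = 9.1% | 2/12 = 16.7% |
| 12 | 1 | 3 | 1/12 = 8.3% | 1/9 = 11.1% | 4/12 = 33.3% |
| 36 | 1 | 1 | 1/36 = 2.8% | 1/35 = 2.9% | 2/36 = 5.6% |
| 36 | 2 | 3 | 2/36 = 5.6% | 2/33 = 6.1% | 5/36 = 13.9% |

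With u = 0 the three figures coincide.

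**Step 4: transient or persistent.** Take a subject who is nAb positive at Cycles 3 and 5 (Weeks 5 and 9, so 4 weeks apart, below the 16-week limit) and whose final sample is ADA positive with nAb NR. NR is not a positive, so Table 9 as written gives transient. If the last valid nAb result is used, the subject is persistent.

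**Step 5: a screen-NR final sample.** If the last ADA assessment means the last record, NR and Negative both count as not positive. If it means the last valid ADA result, the sample is skipped. Correcting Table 8 changes 0 of 4,080 sequences under either reading. Only if the term is defined as the last valid nAb result does the Table 8 row matter: 105 sequences then move, all from transient to persistent.

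**The case against.** The sentence before Table 8 already limits derivation to ADA-negative samples, so a programmer who follows it would code the row correctly. Table 8's two explicit no-result rows stay NR. The sentence on reportable titers does not contain the word only, and Table 8's Positive rows do not depend on titer, so positive-TNR samples may well be tested. The footnotes to protocol Table 2 let PK, ADA and biomarker samples from the same time point substitute for one another when volume is short, which lowers the chance of missing results. The endpoint is descriptive and no test or dose rule uses nAb. A subject listing gives ADA and nAb status for every ADA ever-positive subject.

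Most of this stands, and it rules out several stronger readings that a reader might infer:

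- *The SAP turns missing nAb results into negatives generally.* It does so at sample level only for a screening no-result.
- *The Table 8 error lowers nAb incidence.* Step 2 shows that it cannot.
- *A screen-NR final sample makes a persistent subject transient because it is derived as Negative.* Step 5 shows that the derivation makes no difference unless the last assessment is redefined.
- *nAb incidence is understated.* It may be. The documents give no count of untested ADA-positive subjects, and the number may be zero.

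The objection does not remove the conflict between Table 8 and its own lead-in, and it does not reach Table 9. No sentence in 16.2 qualifies the never-positive row, and the listing does not correct the tabulated percentages.

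**Conclusion.** Wrong as written, with minor consequences. Table 8 contradicts the rule it implements for screen-NR samples, with no effect on incidence by itself. Table 9 classes ADA-positive subjects without a valid nAb result on any ADA-positive sample as never positive, so the ever-positive percentage is a lower bound presented as an estimate. An ADA-positive final sample with nAb NR can likewise move a subject to transient when the positive results span less than 16 weeks. SAP 16.2 is also inconsistent, internally and with protocol 7.6.3, on whether positive-TNR samples are tested, and SAP Section 7 does not list this as a change from the protocol.

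The size depends wholly on the assumed number of untested ADA-positive subjects. One such subject among 12, with one nAb positive, gives 8.3% as written against 9.1% with that subject excluded and an upper bound of 16.7%. None gives no difference.

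**What to change.** 1. **Table 8.** Limit the NA/NA row that gives Negative to samples with a negative screen, and map a screening NR to nAb NR. Add a row for ADA-positive samples, including positive-TNR, that were not tested, giving NR.
2. **Testing sentence.** Align the text before Table 8 with protocol 7.6.3 and the opening of SAP 16.2, so that every ADA-positive sample goes to the nAb assay.
3. **Table 9.** Add a row, nAb not determined, for subjects with an ADA-positive sample, no valid nAb result on any ADA-positive sample and no nAb-positive result, and take them out of never positive. In the 12-subject illustration the rows become 1 ever positive, 1 not determined and 10 never positive.
4. **Last assessment.** Define it for the transient and persistent rows as the last one with a valid nAb result. Make this change together with item 1: under this definition an uncorrected Table 8 would let a failed screen count as a valid final negative.

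The cost is edits to two tables and their surrounding text, plus a small programming change. The output gains one row, and the reported nAb rate may come out slightly higher.

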16.3 Biomarkers (Secondary and CCI Endpoints)

Analysis Set: Biomarker analysis set

Blood samples for mandatory biomarker assessments will be collected at Cycles 1, 3, and 7, and again the the end of treatment visit. CCI

The following are defined as secondary biomarker endpoints:

- Tumor PD-L1 Expression
- Tumor-infiltrating T-cell activity (if fresh tumor samples are available)
- Circulating T-cell number at baseline and confirmed progression
- Circulating B-cell number at baseline and confirmed progression
- Circulating NK-cell number at baseline and confirmed progression

Tumor-infiltrating T-cell activity will be summarized at each scheduled assessment using box plots.

A data listing including all biomarker information collected will be provided.

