		Week 1 (Day 1)	Week 3 (Day 15)	Week 5 (Day 29)	Week 7 (Day 43)	Week 9 (Day 57)	Week 11 (Day 71)	Week 13 (Day 85)	> Week 13 (Day 85)	Within 7 Days of Decision to Discontinue	Visit 30 Days (± 5 days) After Last Tx	Phone Call 90 Days (± 5 days) After Last Tx	Every 12 Weeks (± 1 Week) After Last Tx
Concomitant medications and procedures f	X	Concomitant medications and procedures are collected through the Safety Follow-up Visit									X		
AE collection k		AEs are collected through the Safety Follow-up Visit Treatment-related non-serious AEs are collected until the 90-day Safety Follow-up Phone Call. b										X	
SAE collection k		All SAEs are documented through the 90-day Safety Follow-up Phone Call Ongoing SAEs at the 90-day Safety Follow-up Phone Call will be followed up b										X	
Samples and Laboratory Assessmentsl													
Hematology m	X	X	X	X	X	X	X	X	Q2 weeks	X	X		
Lymphocyte subset quantification n		X		X						X			
Coagulation (hemostaeology) o	X	X	X	X		X		X	Q4 weeks (odd- numbered cycles only)	X	X		
Full serum chemistry p	X	X								X	X		
Core serum chemistry p			X	X	X	X	X	X	Q2 weeks				
Urinalysis q	X	X		X		X		X	Q4 weeks	X	X		
Pregnancy test r	X	X		X		X		X	Q4 weeks	X	X		
T4 and TSH s	X	X		X				X	Q8 weeks	X			
Blood for cytokines t		X	X	X		X				X			
Blood for vaccination-related antibodies u		X						X		X			
HBV and HCV screening tests v	X												

		Treatment Period* (-3/+1 days) 1 Cycle = 14 Days								End Of Treatment/Follow-Up b			
Assessments	Screening (≤ 28 Days Prior to Enrollment)	Cycle 1	Cycle 2	Cycle 3	Cycle 4	Cycle 5	Cycle 6	Cycle 7	Until EOT	EOT/ Withdrawal Visit b	Safety Follow-up c		Survival Follow-up d
		Week 1 (Day 1)	Week 3 (Day 15)	Week 5 (Day 29)	Week 7 (Day 43)	Week 9 (Day 57)	Week 11 (Day 71)	Week 13 (Day 85)	> Week 13 (Day 85)	Within 7 Days of Decision to Discontinue	Visit 30 Days (± 5 days) After Last Tx	Phone Call 90 Days (± 5 days) After Last Tx	Every 12 Weeks (± 1 Week) After Last Tx
CCI CCI													
Baseline tumor evaluation/staging (CT/MRI/other established methods) x	X												

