### 4.2 Secondary Objectives

#### Phase I

- To assess antitumor activity of avelumab by determining the ORR according to RECIST 1.1 and as adjudicated by the Investigator in pediatric subjects with solid tumors and lymphoma treated with avelumab
- To assess progression-free survival (PFS) based on Investigator assessments, duration of response (DOR), time to respond (TTR), and overall survival (OS)
- To characterize the PK of avelumab
- To assess the immunogenicity of avelumab

- To evaluate PD-L1 expression; tumor-infiltrating T-cell activity; T-cell population; and T-cell, B-cell, and NK-cell numbers in tumor tissue at Baseline and at confirmed progression (if tumor tissue is obtained)
- To measure changes in vaccination-related antibody concentrations (diphtheria, tetanus, and pneumococcal conjugate)

CCI

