#### Phase I

- Confirmed BOR according to RECIST 1.1 and as adjudicated by the Investigator
- DOR, TTR, PFS per RECIST 1.1 and as adjudicated by the Investigator, and OS
- Occurrence and severity of TEAEs, AEs of special interest, and treatment-related AEs, and incidence of laboratory abnormalities, as graded by NCI-CTCAE v4.03
- Vital signs (including blood pressure and heart rate)
- Single- and multiple-dose PK profiles of avelumab (ie,  $C_{max}$ , AUC,  $t_{1/2}$ , and  $C_{trough}$ , as data permit)
- Immunogenicity as measured by avelumab ADA, including NABs
- Assessment of tumor PD-L1 expression; tumor-infiltrating T-cell activity; T-cell population; and T-cell, B-cell, and NK-cell numbers at Baseline and at confirmed progression (if tumor tissue is obtained)
- Vaccination-related antibody concentrations.

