### 8.5.3.6 Phase I and Phase II: Biomarkers

Summary statistics for PD-L1 expression and infiltration by lymphocyte subpopulations in tumor tissue will be provided for all preplanned time points, separately for each dose level, and overall. Changes to baseline levels will also be presented as applicable. Profiles over time will be displayed on a per-subject basis.

Details of the statistical analysis of biomarkers will be presented in the SAP.

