	To evaluate programmed death ligand (PD-L1) expression; tumor infiltrating T-cell activity; T-cell population; and T-cell, B-cell and NK-cell numbers in tumor tissue at Baseline and at confirmed progression (if tumor tissue is obtained)	
Secondary Endpoint:
 
 Assessment of tumor PD-L1 expression; tumor-infiltrating T-cell activity; T-cell population; and T-cell, B-cell, and NK-cell numbers at Baseline and at confirmed progression (if tumor tissue is obtained) 	16.3 Biomarkers

	Objective	Endpoint	IAP section
	To measure changes in vaccination-related antibody concentrations (diphtheria, tetanus, and pneumococcal conjugate)	Secondary Endpoint: 
Vaccination-related antibody concentrations	16.4 Vaccination-related antibody concentrations

6 Overview of Planned Analyses

This document covers the avelumab standards for analyses of efficacy and safety. There are no interim analyses for efficacy planned for this trial, but ad hoc interim analyses may be conducted if necessary. There will be periodic safety review by the safety monitoring committee (SMC). The SMC will be responsible for reviewing the safety data and output containing the following information:

- The number and proportion of subjects in the DLT Analysis Set who experienced a DLT during the DLT evaluation period (first two cycles or 28 days of study treatment)
- The number and proportion of TEAEs experienced by subjects in the DLT Analysis Set during the DLT evaluation period
- The number and proportion of TEAEs \geq Grade 3 experienced by subjects in the DLT Analysis Set during the DLT evaluation period.

The SMC will also review patient profiles.

All final, planned analyses identified in the Clinical Trial Protocol and in this IAP will be performed after the last subject has completed his or her end of treatment visit or has been transferred off the trial, and all study data is in-house, all data queries are resolved, and the database is locked.

Statistical analyses will be performed using cleaned eCRF data as well as external data including laboratory data.

7 Changes to the Planned Analyses in the Clinical Trial Protocol

The statistical methods specified in this document are in accordance with protocol version 2.0 (dated 15 September 2017).

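### SAP 16.3 defines the secondary T-, B- and NK-cell numbers as circulating counts, while the objective mapped to it specifies tumor tissue, and SAP Section 7 does not declare the change

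*SAP*

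**What the plan says.** The SAP Section 5 objective concerns, among other items, "T-cell, B-cell and NK-cell numbers in tumor tissue at Baseline and at confirmed progression". Protocol Section 4.2 has the same objective. The matching secondary endpoint in Protocol 8.3.2 does not repeat the tissue qualifier for the counts but keeps the condition: "T-cell, B-cell, and NK-cell numbers at Baseline and at confirmed progression (if tumor tissue is obtained". The endpoint in SAP Section 5 follows it.

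Protocol 8.5.3.6 states the planned analysis: "Summary statistics for PD-L1 expression and infiltration by lymphocyte subpopulations in tumor tissue will be provided for all preplanned time points", by dose level and overall. It leaves further detail to the SAP.

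SAP Section 5 refers this objective to SAP 16.3. That section lists five secondary biomarker endpoints. Two are tumor-based (PD-L1 expression and tumor-infiltrating T-cell activity). Three are blood-based: "Circulating T-cell number at baseline and confirmed progression", "Circulating B-cell number at baseline and confirmed progression" and the equivalent for NK cells. It specifies box plots for tumor-infiltrating T-cell activity and a listing of all biomarker data collected.

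The protocol also schedules a blood assay of the same cell types. The row "Lymphocyte subset quantification" in Protocol Table 1 is marked at Cycle 1, Cycle 3 and End of Treatment, and Sections 7.1.1 and 7.1.3.1 confirm that the sample is blood.

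**The concern.** A count of lymphocytes in peripheral blood does not measure how many lymphocytes have infiltrated the tumor. If 16.3 is followed as written, the cell-number part of the objective is answered with a different quantity, and the tumor-infiltrate summary planned in Protocol 8.5.3.6 is lost. SAP Section 7 states that the methods accord with protocol version 2.0. It then sets out changes to analysis-set definitions, down to small changes of wording, so a reader would take its silence on this point to mean that nothing had changed.

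**Working it through.** No arithmetic applies. The check is a comparison of text in four steps.

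**1. Which compartment each section names for the cell numbers**

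| Place | Compartment | Time points |
|---|---|---|
| Protocol 4.2, objective | Tumor tissue | Baseline; confirmed progression if tissue is obtained |
| Protocol 8.3.2, endpoint | Not named for the counts, but conditional on tissue | As above |
| Protocol 8.5.3.6, analysis | Tumor tissue (infiltration) | All preplanned time points |
| SAP 5, objective | Tumor tissue | As Protocol 4.2 |
| SAP 5, endpoint | As Protocol 8.3.2 | As above |
| SAP 16.3, endpoint | Circulating | Baseline and confirmed progression |
| Protocol Table 1, 7.1.1, 7.1.3.1 (assay schedule) | Blood | Cycle 1, Cycle 3, End of Treatment |

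The endpoint wording alone is ambiguous, but its condition on obtaining tumor tissue would serve no purpose for a blood count. Read with the objective and 8.5.3.6, it means tissue. SAP 16.3 keeps the tissue time points and changes the compartment.

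**2. Which components of the SAP Section 5 objective have a specified analysis**

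- PD-L1 expression: yes. It is an endpoint in 16.3, and status is tabulated at five cut-offs in SAP 11.3.
- Tumor-infiltrating T-cell activity: yes, box plots in 16.3.
- T-cell population: not named in 16.3.
- T-, B- and NK-cell numbers in tumor tissue: not named in 16.3. At most they would appear in the general listing.

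So two of four components are covered and two are not. Counted by the 16.3 list, three of its five secondary biomarker endpoints are blood counts. No summary is specified for those three either, beyond the listing.

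**3. Whether a blood draw exists at confirmed progression**

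Confirmed progression is a reason to stop treatment (Protocol 5.5.1). The End of Treatment visit falls within 7 days of the decision to stop and includes the lymphocyte-subset sample (7.1.3.1). For subjects who stop at confirmed progression, that draw serves. It does not serve subjects who stop for another reason, or those treated beyond confirmed progression under 6.2.1. The circulating endpoint can therefore be met only for part of the population.

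**4. Whether the change is declared**

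SAP Section 7 covers the PK, immunogenicity and biomarker analysis sets and does not mention tumor versus circulating counts. The modification history for 16.3 records a move to box plots and the dropping of cytokines and circulating proteins, nothing on compartment.

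**The case against.** The strongest reply is that 16.3 simply describes the assay that the protocol visibly schedules. The protocol endpoint's wording for the cell counts is close to that of Table 1 footnote n, which defines the blood assay, so the ambiguity starts in the protocol. This explains how the mismatch could arise. It does not remove it, because the objective in both documents and Protocol 8.5.3.6 name tumor tissue.

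Redaction is a second reply. Text is blacked out in SAP 16.3, and so is the tissue section of Protocol 7.6 to which 7.1.1 refers. A provision for tumor lymphocytes there cannot be fully excluded. It would still leave the visible list of secondary endpoints at odds with Section 5.

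Four stronger readings are tempting and are not supported:

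- *That the objective is not analysed at all.* Its PD-L1 and T-cell activity components are.
- *That blood data are passed off as tumor data.* SAP 16.3 labels each count as circulating. The fault is the mapping from Section 5, not a concealed compartment.
- *That no blood draw exists at confirmed progression.* End of Treatment provides one for subjects who stop for that reason.
- *That the 16.3 visit list (Cycles 1, 3, 7 and End of Treatment) contradicts Table 1.* That list covers mandatory biomarker blood samples in general. Table 1 has lymphocyte subsets at Cycles 1 and 3 and End of Treatment, and vaccination antibodies at Cycles 1 and 7 and End of Treatment; together these give the same visits. The text does not say that this is the intended grouping, but no conflict is shown.

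**Conclusion.** The point stands for the cell-number component. SAP 16.3 specifies circulating T-, B- and NK-cell numbers where the protocol objective, Protocol 8.5.3.6 and the SAP Section 5 objective specify tumor tissue, and Section 7 is silent. That component and T-cell population have no visible specified analysis beyond a general listing.

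The consequence is limited. This is part of one descriptive secondary objective in a Phase I population planned at 12 to 36 subjects, with no test or dose decision attached. Tissue at progression is optional (Protocol 7.1.3), so few paired samples can be expected. It is still worth correcting, because as written the reported quantity would not be the one the objective names.

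The conclusion assumes that the redacted text holds no tumor-lymphocyte analysis. It does not assume that tissue counts were assayed, since no visible text says whether they were.

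**What to change.** In SAP 16.3, define the secondary endpoint as T-, B- and NK-cell numbers in tumor tissue, at Baseline and at confirmed progression where tissue exists, with the summary that Protocol 8.5.3.6 plans. State how T-cell population is handled. Report circulating counts as a separate additional endpoint at the Protocol Table 1 visits (Cycle 1, Cycle 3, End of Treatment), and do not label End of Treatment as confirmed progression, since the two coincide only for some subjects.

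If tissue counts were not assayed, say in Section 7 that this component is not analysed, and do not map circulating counts to the tumor-tissue objective in Section 5.

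The cost is SAP wording and, if tissue data exist, a small added output. The biomarker analysis set in SAP 8.2 already admits subjects with a tumor sample, so no new analysis set is needed. The drawback is that paired tissue will be sparse and the results descriptive only.
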